The Effect of Early Prone Position on Prognosis in
Acute Respiratory Failure Due to COVID-19
Pneumonia

05.06.2020

Our study was planned retrospectively in 5 Covid Cohort intensive care units in our hospital to include the dates 15.03.2020 / 15.05.2020. The study started after getting approval from the local ethics committee of our hospital, ethics committee of the Ministry of Health and registering to Clinical Trials. Written and verbal consent was obtained from the patients themselves and / or their legal heirs.

The data of patients over 18 years old who were followed up and treated in the intensive care unit due to acute respiratory failure due to Covid 19 pneumonia were retrospectively reviewed.

Patients who developed acute respiratory failure due to Covid-19 pneumonia and received conventional oxygen therapy with reservoir mask oxygen at the stage of admission to the intensive care unit were included in the study.

patients with respiratory acidosis ($\text{pH} < 7,30$ and $\text{PaCO}_2 > 50$ mmhg), P / F ratio below 150, Glaskow Coma Score (GKS) below 12 points, hemodynamic instability, primary pulmonary pathologies other than pneumonia (lung cancer, cardiopulmonary edema, carcinogen syndrome, etc.) were excluded. patients who underwent NIMV or intubated from admission to intensive care, and those who underwent self PP under 12 hours were not included in the study.

The diagnosis of Covid-19 was made by PCR (Polymerase Chain Reaction) test. The diagnosis of pneumonia was made with clinical findings and the presence of multifocal ground-glass opacities that formed consolidation on computed tomography.

Acute respiratory failure; Despite the conventional oxygen treatment applied at 6 lt / min with a reservoir mask, it was defined as the P / F ratio being less than 300.

The first group (EPP) created for our study was composed of patients who received PP at least 12 hours early (with the first 48 hours) with the oxygen support of the reservoir mask, and the

second group (non-EPP) patients who received oxygen with the reservoir mask but could not be applied early PP due to the patient's incompatibility or rejection.

The demographic data of all patients, gender, body mass index (BMI) and additional diseases (Diabetes Mellitus, hypertension, coronary artery disease, Chronic Obstructive Pulmonary Disease, Congestive heart failure, Chronic kidney failure, etc.) were recorded.

Conventional oxygen therapy applied to all patients was given with a reservoir mask, aiming at SpO₂ 93% and above, at a flow rate of 6-15 L / min. Despite all the treatments, the patients who have a follow-up with a respiratory acidosis (Ph<7,30 and PaCO₂>50 mmhg), SpO₂ value below 93%, applied NIMV, in case of insufficient patient intubated and have invasive mechanical ventilation. In patients who had regression of GKS during follow-up, orotracheal intubation was performed and invasive mechanical ventilation was performed. The number of patients in need of intubation and the number of days they were separated from the ventilator were recorded.

The duration of hospitalization and short-term mortalities of all patients were recorded. Short-term mortality; ICU hospitalization and post-ICU service hospitalization or death up to 28 days in patients discharged home.

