The Effect of Early Prone Position on Prognosis in
Acute Respiratory Failure Due to COVID-19
Pneumonia

05.06.2020

Statistical Analysis:

The data were evaluated using the Windows SPSS 22 package program. Descriptive findings number and percentage distributions for categorical variables; numerical variables are given as mean and standard deviation.

As statistical analysis, Mann-Whitney U test was used for categorical variables, chi-square, normal distribution conditions for numerical variables, Kolmogorov-Smirnov, histogram, and Q – Q Plots graph. Significance level was accepted as $p < 0.05$.

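### The 12-hour proning rule removes early failures from the EPP side only, and no common time rule in the SAP corrects this; the size and net direction are unknown

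*Protocol*

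**What the plan says.** The relevant text is in the protocol's exclusion and group-definition paragraphs, its outcome paragraphs, and the SAP's single section.

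- **EPP group:** "patients who received PP at least 12 hours early (with the first 48 hours"), with oxygen by reservoir mask.
- **Exclusion tied to proning time:** "those who underwent self PP under 12 hours were not included in the study".
- **Non-EPP group:** "patients who received oxygen with the reservoir mask but could not be applied early PP", because of incompatibility or rejection. No minimum time alive, on the mask or free of ventilation is stated.
- **Admission screen, both groups:** among other criteria, "P / F ratio below 150, Glaskow Coma Score (GKS) below 12 points, hemodynamic instability", and also "patients who underwent NIMV or intubated from admission to intensive care".
- **Outcomes:** "The number of patients in need of intubation and the number of days they were separated from the ventilator were recorded". Duration of hospitalization and short-term mortality to 28 days are also recorded. No start of follow-up is given for any of them.
- **Analysis:** the SAP names two-group tests ("Mann-Whitney U test was used for categorical variables, chi-square"), normality checks and a 0.05 significance level. It describes no landmark and no exposure that changes over time.

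**The concern.** Group membership depends on what happens after ICU admission. To enter EPP, a patient must stay alive and on the mask long enough to accrue 12 prone hours. That stretch is event-free by construction, and nothing equivalent is stated for the comparator. NIMV, intubation or death before the twelfth hour removes a willing patient from EPP. A refuser with the same event at the same hour stays in non-EPP and counts as a failure.

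At stake is the only group comparison the plan describes. The distortion does not shrink as more charts are added: the estimate settles on the wrong value and the false-positive rate rises. The plan does not provide for reporting the under-12-hour patients, so a reader of the results could not tell a negligible bias from a material one.

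**Working it through.** The documents state no event rate, sample size or failure times, so there is no plan figure to reproduce. Every rate below is an assumption. Failure means NIMV, intubation or death by day 28, and proning is assumed to have no effect.

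**1. Formula.** Let R be the failure risk in both groups and q the share of willing patients who fail before completing 12 prone hours and are dropped. Then observed EPP risk = (R − q)/(1 − q), non-EPP risk = R, and the risk ratio (RR) is the first divided by the second.

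**2. Failures spread evenly (constant hazard).** q = 1 − (1 − R)^(t/28), where t is the number of days needed to qualify. With R = 0.40:

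| t | q | Share of failures (q/R) | EPP risk | RR |
|---|---|---|---|---|
| 0.5 day | 0.0091 | 2.3% | 0.3945 | 0.986 |
| 1 day | 0.0181 | 4.5% | 0.3890 | 0.972 |
| 2 days | 0.0358 | 9.0% | 0.3777 | 0.944 |

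Varying R from 0.20 to 0.60 gives RR 0.984 to 0.989 at 12 hours and 0.936 to 0.955 at 48 hours.

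**3. Failures clustered early.** With R = 0.40, q = 0.05 (12.5% of failures) gives 0.35/0.95 = 0.368 and RR 0.92. q = 0.10 (25% of failures) gives 0.30/0.90 = 0.333 and RR 0.83.

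**4. False positives.** Simulated two-sided chi-square at 0.05, 100 per side before exclusions: about 5.1% with no bias, 5.1% at q = 0.0091, 6.3% at q = 0.0358, 7.4% at q = 0.05 and 16% at q = 0.10. At q = 0.10 the rate goes from about 10% with 50 per side to 27% with 200.

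**5. Mortality alone.** RR = (M − qd)/[(1 − q)M], with assumed 28-day mortality M = 0.30 and d the share of early failures who die. For d = 0.60, RR is 0.991 (q = 0.0091), 0.963 (q = 0.0358) and 0.947 (q = 0.05). For d = 0.75, which is 0.30/0.40, it is 0.986, 0.944 and 0.921.

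**6. Opposite pull.** Let u be the share of willing patients who stop before 12 hours without ever failing and are also dropped. EPP risk becomes (R − q)/(1 − q − u), which equals R when u = q(1 − R)/R = 1.5q. So u of 1.4%, 5.4% or 7.5% cancels q of 0.9%, 3.6% or 5%. A larger u reverses the sign: q = 0.05 with u = 0.15 gives 0.35/0.80 = 0.4375 and RR 1.09.

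**7. Alternative classification.** Suppose early failures during proning are read as incompatible and moved into non-EPP. With equal numbers willing and refusing and q = 0.05, EPP is 0.35/0.95 = 0.368, non-EPP is 0.45/1.05 = 0.429, and RR is 0.86. The asymmetry grows.

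**8. Check of a common time rule.** In a null simulation, the time at which proning is offered was uniform over 0–24 hours, 12 prone hours took 12 or 24 clock hours, hazards were constant or front-loaded (Weibull shape 1, 0.75 or 0.5), and failures before the offer entered neither group. The plan as written gave RR 0.90 to 0.99; a 48-hour landmark gave 1.00.

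**The case against.** **The admission screen already removes patients about to fail.** It may remove many of them. But it applies to both groups, and at admission, so it leaves the asymmetry among those who pass. Reading the NIMV/intubation exclusion as covering later events would remove an outcome the protocol records.

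**Non-EPP may carry an implicit time requirement.** The absence of an event-free period is read from silence. Early proning refers to the first 48 hours, and the text does not say how a refuser ventilated at hour 6 is classified. Counting that patient as non-EPP is the natural reading, not an explicit rule.

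**Brief proners may not be dropped.** Someone who tried proning and could not tolerate it might enter non-EPP as incompatible. This ambiguity stands, but for early failures it enlarges the imbalance.

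**The bias may be trivial or cancelled.** This stands. The documents neither show nor exclude clustering in the first hours, and a modest number of event-free stoppers offsets the effect.

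**Confounding by refusal may matter more.** This also stands. In the same simulation, refusers at 1.25 times the risk give a null RR of about 0.72 to 0.79 as written and 0.78 to 0.80 with the landmark. At 0.8 times the risk the figures are 1.14 to 1.23 and 1.25 to 1.27, so the landmark then lies further from 1. The documents do not establish which way refusal confounds.

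A reader might infer that the study's result is biased towards EPP overall. The documents do not support that: the mechanism has a direction, but its net effect on the result does not follow. A reader might also blame the lack of covariate adjustment. That is a separate gap; adjusting for baseline variables would not restore the early failures removed from EPP.

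**Conclusion.** The point holds as a flaw in how the groups are formed and timed, and it should be fixed. Confidence is high that the mechanism exists and low on its size. With an assumed 40% failure risk and no true effect, the timing mechanism alone gives RR 0.99 to 0.94 under a constant hazard with 12 to 48 hours needed to qualify. It gives 0.92 or lower only if at least 5% of willing patients fail before 12 prone hours. These figures assume that only early failures are dropped and that willing patients and refusers carry equal risk, neither of which the documents establish.

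**What to change.** Delete the under-12-hour exclusion and apply one time rule to both groups.

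- **Main analysis:** include patients who are alive and have had no NIMV or invasive ventilation by 48 hours after ICU admission. Classify them by prone hours completed by then (at least 12 versus fewer). Compare the protocol's own outcomes (intubation, ventilator days, length of stay, 28-day mortality), counted from 48 hours.
- **Repeat** with the comparator limited to documented refusal or incompatibility.
- **Report** the number, reason for stopping and outcome of all under-12-hour patients, and of all patients with events before 48 hours.
- **Optional sensitivity analysis:** a model with proning as a time-dependent exposure, where event times exist. The protocol does not list NIMV times as recorded, so this should not be the main analysis.

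**Cost.** Protocol and SAP wording change and some charts must be re-read. Prone hours are already needed to apply the 12-hour rule; event status at 48 hours must come from the charts. Events before 48 hours leave the main comparison: 0.0358/0.40 = 9% of them under constant hazard, and 32% under an assumed Weibull shape of 0.5, where 1 − 0.6^√(2/28) = 0.128 and 0.128/0.40 = 0.32. Partial proners in the under-12-hour group dilute the contrast, which is why the repeat is needed. Confounding by refusal or incompatibility remains and should be stated with the results.

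### Non-EPP may hold more patients with mildly reduced consciousness, falling GKS is its own route to intubation, and admission GKS is neither listed nor adjusted for, so the intubation comparison may favour EPP for reasons other than proning

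*Protocol*

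**What the plan says.** **Routes to intubation (Protocol, treatment and follow-up paragraph).** The respiratory route runs from acidosis or low saturation through NIMV: "SpO₂ value below 93%, applied NIMV, in case of insufficient patient intubated and have invasive mechanical ventilation". The next sentence adds a second route: "In patients who had regression of GKS during follow-up, orotracheal intubation was performed and invasive mechanical ventilation was performed". That sentence states neither a GKS threshold nor a respiratory criterion.

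**Outcome (same paragraph).** "The number of patients in need of intubation and the number of days they were separated from the ventilator were recorded". The reason for intubation is not among the items listed.

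**Groups (Protocol, group definitions).** EPP needs at least 12 hours of proning within the first 48 hours. Non-EPP patients were on the same oxygen device but "could not be applied early PP due to the patient's incompatibility or rejection". Patients in between are dropped: "those who underwent self PP under 12 hours were not included in the study".

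**Consciousness at entry (Protocol, exclusion criteria).** The exclusion is "Glaskow Coma Score (GKS) below 12 points", so GKS 12, 13 and 14 remain eligible.

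**Baseline data (Protocol, last paragraph before the treatment description).** The list covers demographics, sex, BMI and comorbidities. GKS is not on it.

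**Analysis (SAP, Statistical Analysis).** The tests named are chi-square and Mann-Whitney U. The sentence that assigns them to variable types is garbled, but neither test carries a covariate, and no adjustment, matching or restriction is described.

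**The concern.** Group membership depends on whether a patient could and would lie prone for 12 hours. Reduced alertness may make that less likely, and it may also place a patient closer to the GKS route to intubation. If so, a single baseline characteristic influences both the group a patient enters and one component of the outcome.

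This is more specific than saying that the groups may differ. Adjusting for the demographics and comorbidities the plan does list would not address it, because GKS is not among them. At stake is the interpretation of a lower intubation rate in EPP: some of it could come from who was able to cooperate rather than from proning. Nothing in the plan would show whether this had happened.

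**Working it through.** The documents give no sample size, event rate or effect size, so there is no stated figure to reproduce. What follows is an illustration in which **every rate is assumed**.

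**Inputs**
- r: risk of respiratory intubation, the same in both groups (no respiratory effect of proning); 20%, 30% or 40%.
- s: share with GKS 12-14 at admission, as EPP vs non-EPP; 0 vs 10%, 0 vs 20%, 5% vs 20%, or 5% vs 40%.
- q: risk of GKS-triggered intubation in those patients; 10%, 30% or 50%.
- Risk of GKS-triggered intubation in all other patients: 2%.

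**Formulas**
- GKS-triggered risk in a group: g = s·q + (1 − s)·0.02
- All-cause intubation: P = 1 − (1 − r)(1 − g)
- Difference, non-EPP minus EPP: (1 − r)(s_non − s_EPP)(q − 0.02)

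**Middle case** (r = 30%, shares 5% vs 20%, q = 30%)
- EPP: g = 0.05 × 0.30 + 0.95 × 0.02 = 0.034; P = 1 − 0.70 × 0.966 = 32.4%
- Non-EPP: g = 0.20 × 0.30 + 0.80 × 0.02 = 0.076; P = 1 − 0.70 × 0.924 = 35.3%
- Difference: 0.70 × 0.15 × 0.28 = 2.9 points; risk ratio for EPP 0.92

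**Smallest case** (r = 40%, shares 0 vs 10%, q = 10%): 0.60 × 0.10 × 0.08 = 0.5 points (41.2% vs 41.7%); risk ratio 0.99.

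**Largest case** (r = 20%, shares 5% vs 40%, q = 50%): 0.80 × 0.35 × 0.48 = 13.4 points (23.5% vs 37.0%); risk ratio 0.64.

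**Chance of p < 0.05 with no respiratory effect.** This uses the two-sided normal approximation for two proportions with n per group: Φ((d − 1.96·s0)/s1) + Φ((−d − 1.96·s0)/s1). Here d is the difference, s0 the pooled and s1 the unpooled standard error. The SAP does not state sidedness; two-sided is assumed. The group sizes are also assumed.

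| Case | Difference | n = 100 per group | n = 200 per group |
|---|---|---|---|
| Equal shares (10% vs 10%) | 0 | 5% | 5% |
| Smallest | 0.5 points | 5.1% | 5.1% |
| Middle | 2.9 points | 7.2% | 9.5% |
| Largest | 13.4 points | 54% | 84% |

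**What the fix does in this model.** Among patients with GKS 15, s = 0 in both groups. At r = 30%, P = 1 − 0.70 × 0.98 = 31.4% in each, a difference of 0. This holds by construction and says nothing about other confounding.

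**Reading.** In this model the difference is against non-EPP whenever that group has the larger share with GKS 12-14 and those patients carry the higher GKS-triggered risk. If the shares are equal, it vanishes.

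**The case against.** Several stronger readings are tempting, and the documents do not support them.

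- **That the Protocol places patients too impaired to cooperate in non-EPP.** It does not say so. Incompatibility is undefined and may mean discomfort, intolerance or anxiety; refusal is a separate reason that needs no impairment. The GKS exclusion removes the most impaired patients. The number with GKS 12-14 is not given and could be near zero. Concentration in non-EPP is a possibility, not a stated fact.
- **That intubation for falling GKS has nothing to do with the lungs.** The Protocol attaches no respiratory criterion to that route, but it does not call it independent of gas exchange either. Falling consciousness can follow hypoxaemia or hypercapnia, so discarding these events could discard genuine respiratory deterioration.
- **That all-cause intubation is the wrong outcome.** The title asks about prognosis, and no primary endpoint is named. All-cause intubation is a legitimate prognosis outcome and should not be replaced.
- **That a lower intubation rate in EPP could never be read as a respiratory benefit.** Under the assumed inputs the bias runs from negligible to large, and the largest case needs 40% of non-EPP to have reduced consciousness.

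Two further objections stand in part. Poor cooperation may also affect how well NIMV is tolerated, so respiratory-trigger intubation would not be free of the same selection. And a variable that is not listed may still have been recorded; whether the charts give a reason for each intubation is not stated.

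What remains is that the plan has two routes into one count, groups formed by cooperation or refusal, GKS 12-14 admitted, and no planned step that would detect or remove an imbalance in GKS.

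**Conclusion.** The concern holds as a possible bias whose direction is conditional. If patients with GKS 12-14 are more common in non-EPP and more often intubated for falling GKS, the intubation comparison will favour EPP for reasons other than proning. Its size cannot be fixed from the documents: about 0.5 to 13 points under the assumed inputs, with 2.9 points in the middle case. It rests on two unverified assumptions: that reduced alertness is part of what incompatibility covers, and that it raises the chance of GKS-triggered intubation. Admission GKS by group and a table of intubation triggers would confirm or dismiss the concern. It is one component of the wider confounding that comes from forming groups by cooperation or refusal.

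**What to change.** 1. Carry admission GKS into the data set and report it by group. It had to be read to apply the exclusion, and it precedes proning, so adjusting for it does not adjust away an effect of treatment.
2. Keep all-cause intubation as the main comparison, and either adjust it for admission GKS or repeat it in patients with GKS 15.
3. State what incompatibility covered.
4. Where charts permit, tabulate the trigger of each intubation as respiratory, GKS regression, or mixed or unclear, classified without knowledge of group if possible. Show respiratory-trigger intubation as a supportive analysis, with GKS-triggered intubation and death as competing events.

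The cost is one or two extra fields from records already under review, and an extra table. Some triggers will be unclear, and the GKS 15 subset will be smaller and less precise. Other confounding from the way the groups are formed remains. No change to care is implied.

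### Ventilator-separation days appear to be recorded only in intubated patients, a subgroup formed after proning, so comparing the two groups on them can be biased in a direction the documents do not fix

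*Protocol*

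**What the plan says.** The measure appears once, in the protocol's closing text on oxygen therapy and follow-up: "The number of patients in need of intubation and the number of days they were separated from the ventilator were recorded". The pronoun refers back to the patients in need of intubation. The sentence that follows, on length of stay and short-term mortality, switches to all patients. No time origin is given for the day count, and there is no value for patients never intubated and no rule for those who die on the ventilator.

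The protocol's group definitions set exposure early. The early-prone group (EPP) is "patients who received PP at least 12 hours early (with the first 48 hours) with the oxygen support of the reservoir mask". The comparison group (non-EPP) is those "who received oxygen with the reservoir mask but could not be applied early PP due to"; the reasons given are incompatibility or refusal.

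The exclusions remove "patients who underwent NIMV or intubated from admission to intensive care". A separate exclusion covers short proning: "those who underwent self PP under 12 hours were not included in the study". Intubation in the analysed patients therefore comes later, after deterioration: the protocol describes patients "applied NIMV, in case of insufficient patient intubated and have invasive mechanical ventilation", and adds: "In patients who had regression of GKS during follow-up, orotracheal intubation was performed".

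The SAP's only text on tests begins: "As statistical analysis, Mann-Whitney U test was used for categorical variables, chi-square". The wording is scrambled. The sensible reading is chi-square for categorical variables and Mann-Whitney for numerical ones. No outcome, analysis population or adjustment is named.

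**The concern.** Intubation is both an outcome that early proning might change and the entry condition for the ventilator-day measure. If proning changes which patients reach intubation, the intubated EPP patients and the intubated non-EPP patients are differently selected. Their ventilator days can then differ with no effect of proning on duration. Correct handling of deaths would not cure this, and neither would perfect balance at admission.

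At stake is a reported finding on time to ventilator separation, in either direction, that readers would take as an effect of proning when it may only reflect who was intubated.

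**Working it through.** The documents give no sample size, intubation rate or ventilator-day figure, so there is nothing of the plan's own to reproduce. Every rate below is an assumption.

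**Model A: the selection mechanism alone.** Groups are identical at admission, nobody dies, and proning has no effect on duration.

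- Severity S ~ N(0,1). A patient is intubated if S + e exceeds a threshold, with e of SD 0.5. The threshold gives 40% intubated in non-EPP and 20% or 30% in EPP, so mainly the milder cases are spared.
- Days = exp(log 10 + b·S + error of SD 0.5), the same formula in both groups, with b = 0.3 or 0.5.

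Mean severity among the intubated is φ(z)/p divided by √1.25, where p is the proportion intubated, z its normal cut-off and φ the normal density:

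- p = 40%: (0.3863/0.40)/1.118 = 0.864
- p = 30%: (0.3477/0.30)/1.118 = 1.037
- p = 20%: (0.2800/0.20)/1.118 = 1.252

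The ratio of typical days is then about exp(b × difference in mean severity). For 40% vs 20% the difference is 0.388, so the ratio is exp(0.116) = 1.12 at b = 0.3 and exp(0.194) = 1.21 at b = 0.5. Simulation agrees:

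| Intubated, non-EPP vs EPP | b | Median days, non-EPP vs EPP | Shift | Mann-Whitney rejection at 5% |
|---|---|---|---|---|
| 40% vs 20% | 0.3 | 12.9 vs 14.5 | +1.6 | about 9% (60 per group), 12% (100) |
| 40% vs 20% | 0.5 | 15.3 vs 18.6 | +3.3 | about 14% (60 per group), 20% (100) |
| 40% vs 30% | 0.3 | 12.9 vs 13.6 | +0.7 | 6–9% over both slopes and sizes |
| 40% vs 30% | 0.5 | 15.3 vs 16.7 | +1.4 | (as above) |

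**What happens to the direction when Model A's assumptions change.**

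- Intubations averted at random (b = 0.3, 0.5): 12.9 vs 13.0 and 15.3 vs 15.3. No bias.
- Non-EPP patients 0.5 SD sicker, same thresholds, 40% vs 30% case: 13.9 vs 13.6 and 17.2 vs 16.7. The sign reverses. Against the 20% case the gap only shrinks (13.9 vs 14.5; 17.2 vs 18.6).

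**Model B: a second set of assumptions.** Median about 9 days, b = 0.3, capped at 28 days, intubation lowered from 40%, 50% or 60% to 30%. Figures are mean days, EPP minus non-EPP, among the intubated; again there is no true effect on duration.

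- Mildest averted, no deaths: +0.5, +1.0, +1.35.
- Most severe averted, no deaths: −0.75, −1.1, −1.35.
- Mildest averted, about 50–60% dying on the ventilator, days counted to separation or death: −0.1 to −0.2.
- 50% vs 30%, mildest averted, no deaths, with the fastest-progressing 25% or 40% of intubated EPP patients removed (as the exclusion of short proning might do): +0.25 and 0.0.

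**Effect of the population chosen (Model B, 50% vs 30%, mildest averted).** Ventilator-free days to day 28, with 0 for death after intubation and 28 for patients never intubated (assumed alive), differ by +2.1 days for EPP in all patients without deaths and by +3.6 with deaths. Restricted to the intubated, the same scenarios give −1.0 and −1.5. Changing only the population reverses the sign.

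**The case against.** The strongest reply is that no document commits to the criticised test. The protocol says only that the days were recorded, and the SAP names no outcome. That stands: the comparison is inferred. But the study has two groups, records this variable, and lists a two-group test for numerical variables without exempting any outcome, so following the plan would most naturally produce it.

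A second reply is that the measure might be ventilator-free days, which can be defined for everyone. One ambiguous sentence does not rule this out. The plain reading is against it, and if it was intended the documents need to say so.

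A third concerns direction. A reader might infer that the bias probably works against proning, so that the better proning prevents intubation the worse it looks on ventilator time. The documents do not support this. It requires that mainly milder cases are spared, and nothing says which intubations are averted. It can also be offset or reversed if days stop at death, if patients who refused proning were sicker, or if excluding those proned for under 12 hours removed fast progressors. These features are possible, not established. They rule out a stated direction, but they do not make the comparison interpretable, since one bias cannot be relied on to cancel another.

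Finally, the larger figures need intubation to be halved. At 40% vs 30% the excess over 5% is small.

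**Conclusion.** The point holds as a fault of population and definition. On the plain reading the ventilator measure is confined to a subgroup formed after exposure, and nothing in the plan prevents a group test within it. If proning changes who is intubated, that test does not estimate an effect of proning on ventilator time.

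The size is illustrative only: a spurious shift of about 0.7 to 3.3 days and a rejection rate of about 6% to 20% against a nominal 5%. This assumes milder cases spared, no deaths, groups identical at admission, 60 or 100 patients per group, and 20–30% intubated against 40%. Other equally admissible assumptions give no bias or the opposite sign. Two claims go too far: that the bias is known to disfavour proning, and that the SAP explicitly plans this test.

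**What to change.** In the SAP:

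1. Define the ventilator measure: its time origin, its horizon and how death before separation is handled.
2. Do not test EPP against non-EPP on ventilator days among intubated patients. Report those days descriptively by group, with the number intubated and the number who died before separation.
3. Make the group comparison in all patients. One option is the proportion alive and off invasive ventilation 28 days after ICU admission, with never-intubated survivors counted as off ventilation. Another is 28-day ventilator-free days with death ranked worst.
4. State that the intubated-only figures are not evidence of a proning effect, and that this change does not remove confounding between the non-randomised groups.

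The cost is small but is more than wording. Intubation, separation and death are already recorded, but the protocol states a 28-day horizon for mortality only, so ventilator status at day 28 must be derived from the existing records. The all-patient measure is also less specific to weaning.

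### The intubation count has no time window, no definition of need and no rule for death without intubation, so unequal unintubated deaths would distort the group comparison

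*Protocol*

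**What the plan says.** The outcome at issue is "The number of patients in need of intubation". The protocol's full sentence is "The number of patients in need of intubation and the number of days they were separated from the ventilator were recorded". It sets no time limit, does not say whether need means a tube placed or criteria met, and does not say how to classify a patient who dies first.

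Patients already on NIMV or intubated at ICU admission are excluded, so everyone starts on mask oxygen. The protocol then gives two routes to a tube. For worsening gas exchange, patients were "applied NIMV, in case of insufficient patient intubated and have invasive mechanical ventilation". Separately, "In patients who had regression of GKS during follow-up, orotracheal intubation was performed".

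Deaths are a separate outcome: "The duration of hospitalization and short-term mortalities of all patients were recorded". The definition of short-term mortality includes "death up to 28 days in patients discharged home", but the day from which the 28 days run is not clear.

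The comparator group consists of patients not proned early because of "incompatibility or rejection".

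The SAP's Statistical Analysis section offers "Descriptive findings number and percentage distributions for categorical variables", then a sentence naming chi-square and Mann-Whitney U whose assignment to variable types is hard to parse, and a 0.05 significance level. It ties no test to intubation by name and contains no composite, time-to-event or competing-risk analysis. Neither document names a primary outcome.

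**The concern.** Intubation is read as a marker of respiratory failure, but it can be observed only in patients who live long enough, and accept enough treatment, to reach it. If the count goes into a two-by-two table, which is the likely use of the planned chi-square, a patient who dies on mask oxygen or NIMV shares a cell with a patient who went home.

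An imbalance between the groups is plausible here. The early-prone patients tolerated at least 12 hours of prone positioning, while the comparator is made up of patients who could not or would not do so. If such patients also declined or failed to tolerate NIMV or intubation more often, the comparator's intubation count would fall for a reason unrelated to lung recovery. That link is an assumption; the documents neither state it nor exclude it.

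At stake is what a lower intubation proportion means: better lungs, or more deaths before a tube was placed.

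**Working it through.** **Inputs.** The documents give no sample size, effect size, intubation rate or death rate, so there is no planned figure to reproduce. Every rate and group size below is an assumption chosen to show the mechanism.

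**Identity.** In each group let F be the proportion intubated or dead without intubation, D the proportion dead without intubation, and I the proportion intubated. Then I = F − D. For comparator minus early-prone:

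difference in I = (difference in F) − (difference in D).

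The distortion of the risk difference is therefore exactly the imbalance in D.

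**Illustration 1.** Assume 100 per group and F = 30% early-prone versus 45% comparator. The test is a two-sided Pearson chi-square without continuity correction. F itself differs by 15 points, p = 0.028.

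| D, early-prone / comparator | I, early-prone / comparator | Difference in I | p |
|---|---|---|---|
| 5% / 5% | 25% / 40% | 15 | 0.024 |
| 2% / 5% | 28% / 40% | 12 | 0.073 |
| 2% / 8% | 28% / 37% | 9 | 0.17 |
| 2% / 17% | 28% / 28% | 0 | 1.00 |
| 2% / 20% | 28% / 25% | −3 | 0.63 |
| 8% / 2% | 22% / 43% | 21 | 0.002 |

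Equal D leaves the 15 points intact. A 3-point imbalance takes the result across 0.05, a 15-point imbalance removes the difference, and only a larger one changes its sign. An excess of unintubated deaths in the early-prone group exaggerates the apparent benefit.

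**Sensitivity to the assumptions.** At 200 per group with the same proportions, D of 2% versus 5% moves p from 0.002 to 0.011, which is still below 0.05. With F = 25% versus 50% and 100 per group, D of 2% versus 12% leaves 23% versus 38%, p = 0.021, and the sign changes only if the imbalance exceeds 25 points. Whether significance is lost thus depends on the assumed size and effect; the shift in the difference does not.

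**Illustration 2, risk ratios (early-prone / comparator).**
- No true difference, F = 40% in both groups. D of 5% v 10% gives 0.35/0.30 = 1.17; 5% v 15% gives 0.35/0.25 = 1.40; 10% v 5% gives 0.30/0.35 = 0.86.
- True ratio 0.30/0.40 = 0.75. D of 5% v 10% gives 0.25/0.30 = 0.83; 5% v 15% gives 0.25/0.25 = 1.00.

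In the second set the true effect shrinks or disappears; it does not reverse.

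**The case against.** The case on the other side has substance.

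- **The outcome wording.** A reader might infer that the plan scores an unintubated death as a success. Neither document defines success. The protocol speaks of patients who needed intubation, which could include those who met criteria but refused or died first. On that reading D shrinks to deaths that never met criteria. This stands, and it makes the missing definition part of the defect.
- **The pathway.** A reader might infer that intubation comes only after failed NIMV. A falling coma score is a second route, with no mention of NIMV. Both routes lead to a tube, no treatment limits are mentioned, and patients with P/F below 150, a coma score below 12 or haemodynamic instability were excluded at entry. Deaths without a tube may be few. D of 10% to 15% out of F = 40% means that 25% to 37.5% of failing comparator patients were never intubated, which is demanding. This limits the likely size but does not close the gap.
- **Mortality is reported.** An excess of unintubated comparator deaths would tend to show as higher comparator mortality beside a lower intubation count, which would warn the reader. But two separate totals do not show which deaths occurred without intubation, so they cannot correct the comparison.
- **The test.** That intubation is compared by chi-square is the likely reading of the SAP, not something it states.

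**Conclusion.** The point holds as an undefined endpoint with an unhandled competing event. If unintubated deaths go in the not-intubated cell, the intubation risk difference is wrong by exactly the between-group imbalance in those deaths. That part is arithmetic. The size in this study is unknown because the documents give no rates, and the direction depends on which group has more such deaths.

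Two stronger readings are tempting and unsupported. One is that the intubation result is likely to be reversed. Reversal needs an imbalance larger than the true difference, and nothing in the documents makes that probable. The other is that the intubation result cannot be interpreted at all and should be dropped as a test. Equal unintubated deaths leave the risk difference unchanged, mortality is available as a partial check, and no primary outcome is named, so prognosis does not rest on intubation alone.

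The change is still worth making: the gap is real, an imbalance is plausible given how the comparator was formed, and the remedy is cheap.

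**What to change.** 1. Define the intubation endpoint: either intubated, or met the criteria already documented in the protocol whether or not a tube was placed. Count it within 28 days of a stated start point such as ICU admission, and state the same start point for mortality.
2. Keep the intubation comparison. Add intubation or death from any cause by day 28, with a death without intubation counted as an event.
3. A cumulative incidence of intubation with death as the competing event is an acceptable alternative. Show it beside the curve for death without intubation: with complete follow-up, the day-28 value for intubation alone equals the crude proportion and would not solve the problem by itself.
4. Report by group the numbers intubated and the numbers who died without intubation. Add NIMV only if the charts record it; the protocol describes NIMV as given but does not list it among the recorded outcomes.

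The cost is SAP wording, event dates from the charts and one derived variable, since intubation and short-term mortality are already recorded. A composite joins events of unequal weight, which the component rows address. None of this corrects the selection of the comparator group, which needs separate handling.
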